Methods for recruiting subjects: Three sites will participate in this study: 1) JJPVAMC will be the Lead Site and has four ReWalk units; 2) UMROI will be a sub award site and has two ReWalk units with the potential to acquire two additional units through collateral funding and 3) KFRC will be a sub site of the JJPVAMC through the satellite Center of the Spinal Cord Damage Research Center which is located at Kessler Institute of Rehabilitation. KFRC has one Ekso unit. The JJPVAMC and KFRC study sites each have close to 3 years of experience conducting studies using the exoskeletal systems for persons with SCI. UMROI has recently acquired two ReWalk units and has experience conducting a DOD CDMRP Clinical Trial in persons with SCI. UMROI has begun to study the ReWalk in their patients. Potential participants will be recruited from the research databases at each institution and from the clinical outpatient services. At the UMROI site, the principal investigator also is the Director of the SCI support team clinic at the Baltimore VA Medical Center, so he will be able to recruit from both a civilian and a veteran population. Currently, both the JJPVAMC and KFRC have a waiting list of participants who have contacted either Center to become involved an exoskeletal-assisted walking program. All three study sites have a positive and significant history of recruiting and conducting ethically appropriate clinical trials in persons with SCI.

Expected withdrawal rates: In 13 participants enrolled to date at the JJPVAMC, three withdrew (one due to job relocation, one due to an unrelated medical illness, and one due to difficulty with travel). It is expected that these and/or similar reasons will affect the compliance and attendance of this study to some degree. As such a total of 132 participants will be enrolled as follows: JJPVAMC (n=28, T3 and below), KFRC (n=16, T2 and above) and UMROI (n=20, T3 and below). An enrollment schedule by site is provided (**Table 4**).

Table 4. Original Enrollment Schedule by Site

Study Sites and Groups		Y1				Y2				Y3				Y4				Sub Total
		Q1	Q2	Q3	Q4													
JJPVAMC (T3 and below, ReWalk)	Group 1			2			4			4			4					14
	Group 2			2			4			4			4					14
	subtotals			4			8			8			8					28
JJPVAMC at KFRC (C5 to T2, Ekso)	Group 1			2			2			2			2					8
	Group 2			2			2			2			2					8
	subtotals			4			4			4			4					16
UMROI (T3 and below, ReWalk)	Group 1			2			3			3			2					10
	Group 2			2			3			3			2					10
	subtotals			4			6			6			4					20
Total Participants by Year				12		18				18				16				64

Group assignment process: Participants will be block randomized within site.

Statistical Plan and Data Analysis:

The best value achieved for each walking test during sessions 5 to 12 (T1) and from 13 to 36 (T2) will be recorded separately to be used for comparative analysis. These best T1 and T2 scores will be used to determine

percent of occurrence with the hypothesized goals. Achievement of the hypothesized goals in the WALK intervention group for the primary outcomes (10mWT, 6minWT and TUG at the 12- and 36-session time points) will be reported as categorical data and presented as a percent of occurrence with the 95% upper and lower confidence intervals (CI). Continuous variables for the Secondary outcomes of the body composition and bowel function variables will be presented as mean \pm SD. For the continuous variables, a difference score or percent change from pre to post will be calculated for the WALK and UA arms of the study. Comparisons between WALK (Pre-Post) vs. UA (Pre-Post) difference scores will be performed using paired t-tests. Pre to post comparisons for variables that are not normally distributed will be performed by non-parametric tests such as the Wilcoxon signed rank test or the paired sign test.

Walking outcomes (10mWT, 6minWT, and TUG): Achievement of the hypothesized goals in the WALK intervention group will be reported as categorical data and presented as percent occurrence with 95% confidence intervals (CI). For each of these outcomes, the best value achieved during the T1 period (sessions 5-12) and the T2 period (sessions 13-36) will be recorded separately and compared to the hypothesized goals, as listed below:

Primary Hypothesis (are tested pre and post the WALK arm only):

1. By session 36, 70% of the participants compared with 10% at session 12 will be able to perform the 10m WT \leq 40 seconds (\geq 0.25 m/s);
2. By session 36, 70% of the participants compared with 10% at session 12 will be able to perform the 6min WT distance \geq 80 m (\geq 0.22 m/s); and
3. By session 36, 60% of the participants compared with 20% at session 12 will be able to perform the TUG in \leq 90 seconds.

Power Calculation: A one-sample method was chosen to test the observed proportion against the expected proportion determined from the preliminary data of the percent of those who achieved these goals. Using the most stringent criteria above of 20% (session 12) versus 60% (session 36) who achieve the TUG goal, there is 100% power (alpha=5%, double sided Z-power=5.6) with 13 of 63 (20%) versus 38 of 64 (60%) achieving the goal. If the attrition rate is as high as 25%, then the power is still 100%, (alpha=5%, double sided Z-power=4.53), with 10 of 48 (20%) at session 12 versus 29 of 48 (60%) of the participants achieving the goal at session 36.

Secondary Hypotheses

1. Bowel function will improve as demonstrated by 25% improvement on the Ten-question bowel survey.
2. Total body fat mass is hypothesized to be reduced by 2.0 ± 1.2 kg

Power Calculation: The preliminary data demonstrated a total score change of 31.5 ± 7.1 to 22.5 ± 5.3 , N=8 and a total body fat mass change from 24.14 ± 8.45 to 22.22 ± 8.19 , N=9, alpha=0.05, using a pairwise method, the power for both was 100%. Allowing for 25% dropout, the power is still 100% for 48 participants at an alpha=0.05.

Please note, that both the primary and secondary hypotheses are well powered due to the huge effect observed in the preliminary data. However, performing this study in fewer participants will not permit us to ask many of the exploratory questions. There is no empirical data to support an appropriate power calculation for the exploratory hypotheses.

References

2. Spungen, A. M., Adkins, R. H., Bauman, W. A., Kemp, B. J. & Waters, R. L. The effects of level and completeness of lesion on body composition in subjects with spinal cord injury. *J Spinal Cord Med* **22**, 43 (1999).

3. Spungen, A. M., Wang, J., Pierson, R. N. & Bauman, W. A. Soft tissue body composition differences in monozygotic twins discordant for spinal cord injury. *J. Appl. Physiol.* **88**, 1310–5 (2000).
4. Wahman, K. *et al.* Cardiovascular disease risk factors in persons with paraplegia: the Stockholm spinal cord injury study. *J Rehabil Med* **42**, 272–278 (2010).

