The effect of exoskeletal-assisted walking was investigated on bowel function by using three assessments: a Ten Question Bowel Function Survey (10Q BFS), the Bristol Stool Scale (BSS), and the short-form item bank for Bowel Management from the SCI QOL^{21,22} (all questionnaires and survey assessments may be found in the “Surveys” section). The 10Q BFS captures information about the amount of time spent per day and the frequency per week for bowel evacuations, the amount of oral laxatives and stool softener use, frequency of digital stimulation, and frequency of unwanted bowel evacuation episodes. The BSS is an indicator of how hard the stool is and the Bowel Management short form of the SCI QOL assesses the amount of burden. All participants reported improvement for all three measures of bowel function (Figure 3). By session 20, significant improvements in bowel function were reported in 6 participants: reduced total time per bowel evacuation (BE) 78 ± 34 to 33 ± 7 minutes, $p < 0.05$, power=0.98; Bristol Stool Scale (BSS) 2.6 ± 1.1 to 4.2 ± 0.4 , $p < 0.05$, power=0.98, indicating a hard to softer stool consistency; and improved weekly frequency of BE: 2 ± 0.5 to 4 ± 0.5 , $p < 0.05$, power=0.99. Improvement in bowel function continued for all of the training sessions but by one-month after cessation of the walking program the improved bowel function was no longer present²³.

Analysis of the 10Q BFS, BSS, and Bowel Management SCI-QOL was performed in 8 participants before and after 36 sessions (**Figure 3**).

[figure not shown]
Figure 3. Bowel Function results from the preliminary data, N=8.

Pre=before exoskeletal-assisted walking training; Post=after 20 sessions; SCI=spinal cord injured participants; in Panel A, AB=able-bodied controls matched for age \pm 5 years, gender, and ethnicity.

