 - ii. 10% in \leq 40 seconds (\geq 0.25 m/s)
 - b. 6min WT
 - i. 80% at a distance of \geq 50 m (\geq 0.14 m/s)
 - ii. 20% at a distance \geq 80 m (\geq 0.22 m/s);
 - c. TUG
 - i. 80% in \leq 120 seconds
 - ii. 20% in \leq 90 seconds

2. By session 36 (three months of WALK training), participants will have improved their ability to walk faster and longer distances and will be able to perform exoskeletal-assisted walking tests with or without minimal assistance as follows:
 - a. 10m WT - 70% in ≤ 40 seconds (≥ 0.25 m/s)
 - b. 6min WT - 70% at a distance ≥ 80 m (≥ 0.22 m/s)
 - c. TUG - 60% in ≤ 90 seconds.

Secondary Aims are to affect the following by three months of exoskeletal-assisted walking (WALK):

1. To improve bowel function as measured by established survey instruments; and
2. To reduce total body fat mass and percent as measured by DXA.

Exploratory Aims:

1. To improve autonomic/cardiovascular function (vagal tone) measured by high frequency component of the 24-hour holter monitor;
2. In persons with T6 and above, to improve orthostatic hypotension (OH) tolerance measured by a standard OH challenge test from supine to seated;
3. To improve HDL-c, Homeostatic Model of Assessment – Insulin Resistance (HOMA-IR), serum total testosterone and estradiol levels measured by serum and plasma assay kits; and
4. To improve quality of life (QOL) measured by item banks from the SCI-QOL and Patient Reported Outcomes Measurement Information System (PROMIS).

Hypotheses

Primary Hypothesis (are tested pre and post the WALK arm only):

1. By session 36, 70% of the participants compared with 10% at session 12 will be able to perform the 10m WT ≤ 40 seconds (≥ 0.25 m/s);
2. By session 36, 70% of the participants compared with 10% at session 12 will be able to perform the 6min WT distance ≥ 80 m (≥ 0.22 m/s); and
3. By session 36, 60% of the participants compared with 20% at session 12 will be able to perform the TUG in ≤ 90 seconds.

Secondary Hypotheses (are tested between the WALK arm and the UA arm, within-subject)

4. Bowel function will improve by 25% using the Ten-Question bowel survey. (Note, the components of this survey represent a 50% reduction in bowel evacuation (BE) time, a 25% increase in BE weekly frequency per week, a 50% reduction in BE medication use, and/or a 25% improvement in stool consistency from harder to softer.)

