this device is better suited for those with lower thoracic SCI (T3 and below) who can perform weight shifting and clear the foot for stepping. By including both the Ekso (for T2 and above in those who have some spared hand function to hold the crutches or can have them securely attached) and the ReWalk (for T3 and below), the effect of exoskeletal-assisted walking can be investigated across all levels of cervical, thoracic and lumbar SCI.

Study variables to be measured: Baseline screening evaluations for eligibility will include a history and physical examination with a complete International Standards for Neurological Classification of SCI (ISNCSCI) examination [the ISNCSCI includes a full American Spinal Cord Injury Impairment Scale (AIS)], range of motion, Ashworth spasticity examination at selected lower extremity joints, standard orthostatic tolerance test, and bone mineral density (BMD). The primary outcome assessments will consist of the 10m, 6min and TUG walking tests. The walking tests will be performed and recorded for each session of the WALK arm. The secondary outcomes include body composition and bowel function. A full battery of outcome assessments will be performed at baseline and after completion of the intervention of WALK arm (after 36 sessions) and the UA (after 12 weeks) periods. Interim assessments for the SCI QOL will be performed at midpoint, after 18 sessions. Bowel function will be measured bi-weekly throughout both arms of the study (**Table 3**).

Table 3. Schedule of Testing for each Intervention Arm

¹WALK Sessions include heart rate (HR), blood pressure (BP) and Rating of Perceived Exertion (RPE) recordings before, during and after walking and/or more often as clinically indicated.

²WALK Skills include 10m WT, 6min WT, TUG, and assorted mobility skills for turning, stopping, reaching, and navigating doors.

DXA=dual energy x-ray absorptiometry scan; ISNCSCL=International Standards for Neurological Classification of Spinal Cord Injury (SCI); OH BP=postural orthostatic hypotension blood pressure tolerance test; and SCI-QOL=spinal cord injury quality of life surveys.

Description of Assessments

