Mobility Skills: Exoskeletal-assisted walking tests for the 10m WT, 6min WT, and TUG will be performed at least one time per week during the WALK arm intervention. It was observed during the Phase II trial that weekly assessment of the walking tests provided structured feedback to the participants regarding their progress in mastering the use of the powered exoskeleton and was useful in motivating the participants. Additional mobility skills (turning, wall rest, stopping, and navigating doors) will be assessed throughout the WALK arm; but not to be considered as part of the primary outcomes. The walking tests will be performed as per the standardized descriptions^{52,53} with modifications for the exoskeletons. The PI and lead biomedical engineer from the JJPVAMC ([name]) have significant experience and expertise in performing these walking and mobility tests and will travel to the other two sites to train the staff for standardization purposes across the sites during the designated start-up time of the study.

Body Composition: A dual energy x-ray absorptiometry (DXA) scan for regional and total body fat, lean and bone tissue masses will be performed three times: at baseline, at crossover, and after the second arm of the study for both the WALK and UA arm interventions. Standardized DXA scans will be performed as previously described at all three study sites^{2,3,54}.

ISNCSCI: A neurological evaluation for sensory and motor function, level of injury and lower extremity motor scores will be performed according to the ISNCSCI standards⁵⁵. This exam will be performed three times: at baseline, at crossover, and after the second leg of the study for both the WALK and UA arm interventions.

Bowel function surveys: The 10Q Bowel Function Survey (BFS) and the Bristol Stool Scale will be administered before both interventions and then bi-weekly (two times/month) for a total of 16 times during the two arms of the study. This information will be used to determine key components to a participant's weekly bowel regime²³. The Bowel Management item bank short form from the SCI-QOL will be performed three times: at baseline, at crossover, and after the second arm for both the WALK and UA arm interventions. The PI will instruct the three sites on the standardized method for administering these assessments.

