# A Randomized, Crossover Clinical Trial of Exoskeletal-assisted Walking to Improve Mobility, Bowel Function and Cardio-Metabolic Profiles in Persons with SCI

## Statistical Plan and Data Analysis:

The best value achieved for each walking test during sessions 5 to 12 (T1) and from 13 to 36 (T2) will be recorded separately to be used for comparative analysis. These best T1 and T2 scores will be used to determine percent of occurrence with the hypothesized goals. Achievement of the hypothesized goals in the WALK intervention group for the primary outcomes (10mWT, 6minWT and TUG at the 12- and 36-session time points) will be reported as categorical data and presented as a percent of occurrence with the 95% upper and lower confidence intervals (CI). Continuous variables for the Secondary outcomes of the body composition and bowel function variables will be presented as mean  $\pm$ SD. For the continuous variables, a difference score or percent change from pre to post will be calculated for the WALK and UA arms of the study. Comparisons between WALK (Pre-Post) vs. UA (Pre-Post) difference scores will be performed using paired t-tests. Pre to post comparisons for variables that are not normally distributed will be performed by non-parametric tests such as the Wilcoxon signed rank test or the paired sign test.

**Walking outcomes (10mWT, 6minWT, and TUG):** Achievement of the hypothesized goals in the WALK intervention group will be reported as categorical data and presented as percent occurrence with 95% confidence intervals (CI). For each of these outcomes, the best value achieved during the T1 period (sessions 5-12) and the T2 period (sessions 13-36) will be recorded separately and compared to the hypothesized goals, as listed below:

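### The bowel contrast takes Group 1's post-WALK score as its UA baseline, so the expected loss of benefit after WALK inflates the estimated effect, by 50% if reversal is complete

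*Protocol*

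**What the plan says.** **Measurement.** Protocol, Study variables to be measured: "Bowel function will be measured bi-weekly throughout both arms of the study". Under Bowel function surveys, the 10Q BFS and BSS are "administered before both interventions and then bi-weekly (two times/month) for a total of 16 times during the two arms of the study". The use given there is descriptive: "This information will be used to determine key components to a participant's weekly bowel regime".

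**Analysis.** The protocol heads the hypotheses that include bowel function "Secondary Hypotheses (are tested between the WALK arm and the UA arm, within-subject". The SAP (Statistical Plan and Data Analysis, repeated in the protocol) says that "a difference score or percent change from pre to post will be calculated for the WALK and UA arms of the study", and then "Comparisons between WALK (Pre-Post) vs. UA (Pre-Post) difference scores will be performed using paired t-tests". A signed-rank or sign test is the fallback for non-normal variables. No repeated-measures model and no period, sequence or carry-over term is given.

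**Design.** Under Research design, Group 1 has 12 weeks of WALK and then 12 weeks of UA; Group 2 has the reverse order. Allocation is 32 to each group. No washout is stated.

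**Expected reversal.** Preliminary Studies reports that "by one-month after cessation of the walking program the improved bowel function was no longer present". Exploratory Hypothesis 1 predicts the same for Group 1: a return to baseline within one month of UA.

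**Pilot scores.** The secondary power calculation rests on "a total score change of 31.5 ± 7.1 to 22.5 ± 5.3" in 8 participants, where a lower score is better. The target is a 25% improvement.

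**The concern.** A change score needs a starting value that the other treatment has not moved. Group 2 has one for both arms: its UA baseline is study entry, and its WALK baseline follows 12 weeks of usual activity. Group 1 does not. It enters UA directly from WALK, so its UA starting value carries the WALK benefit. When the benefit fades, as the protocol expects, the UA change is a deterioration caused by stopping WALK. Subtracting that deterioration from the WALK change counts the same benefit twice.

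At stake is the size of a secondary effect with a numerical goal. If the 25% goal is judged on the WALK-versus-UA contrast, a smaller true improvement could appear to meet it.

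**Working it through.** **1. The plan's power figure.** Inputs: pilot change 22.5 − 31.5 = −9.0, SDs 7.1 and 5.3, N = 48 after 25% dropout, alpha 0.05 (taken as two-sided). The pre-post correlation r is not given, so 0 to 0.9 was assumed.

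- SD of change = √(7.1² + 5.3² − 2r·7.1·5.3), which is 8.86 at r = 0 and 3.28 at r = 0.9.
- At r = 0 the noncentrality is 9 / (8.86/√48) = 7.04. Paired-t power rounds to 100% there and at higher r, so the stated figure reproduces.
- That is power for a pre-post change. For the WALK-change minus UA-change contrast with a shared crossover value, power for 9 points at N = 48 is still at least 99.7% (assumed intraclass correlation 0.3 to 0.7, two-week autocorrelation 0 to 0.7).

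**2. Expected value of the planned contrast.** Let Δ be the true effect and f the fraction of it lost during UA in Group 1.

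- Group 1: WALK change Δ, UA change −fΔ, contrast (1 + f)Δ.
- Group 2: UA change 0, WALK change Δ, contrast Δ.
- 1:1 average: (1 + f/2)Δ.

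With Δ = −9:

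| Reversal f | Group 1 | Group 2 | Average | Excess |
|---|---|---|---|---|
| 0 | −9.00 | −9 | −9.00 | 0% |
| 25% | −11.25 | −9 | −10.125 | 12.5% |
| 50% | −13.50 | −9 | −11.25 | 25% |
| 75% | −15.75 | −9 | −12.375 | 37.5% |
| 100% | −18.00 | −9 | −13.50 | 50% |

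A simulation with full reversal (N = 48, 4,000 runs, intraclass correlation and autocorrelation both assumed 0.5) gave −13.47. With no true effect it rejected in 5.0% of runs.

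**3. Against the 25% goal.** −9 is 28.6% of 31.5, and −13.5 is 42.9%. A true −5.25 (16.7%) becomes −5.25 × 1.5 = −7.875, which is 25%. On the SAP's percent-change option, Group 1's UA change is +9/22.5 = +40%. Its contrast is then −28.6 − 40 = −68.6 points against −28.6 in Group 2. The average is −48.6, about 70% too large.

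**4. End-of-period levels instead.** Group 1: post-WALK minus post-UA = fΔ. Group 2: Δ. Average: (1 + f)Δ/2. With full reversal this is −9 in both groups. With incomplete reversal at week 12 it is too small, for example 0.75 × (−9) = −6.75 at f = 50%.

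**5. Precision of levels.** With crossover score Y₁₂, entry score Y₀ and final score Y₂₄, the planned Group 1 contrast is 2Y₁₂ − Y₀ − Y₂₄. Under an assumed common correlation r its variance is 6(1 − r)σ², against 2(1 − r)σ² for Y₁₂ − Y₂₄. The change to levels therefore loses no precision.

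**6. Averaging the last three visits.** With adjacent-visit correlation ρ decaying serially and between-arm correlation b, the variance of a single late-visit contrast relative to a three-visit mean is (1 − b) / [(3 + 4ρ + 2ρ²)/9 − b]. Assumed pairs (ρ, b) of (0.9, 0.6), (0.8, 0.5) and (0.7, 0.4) give 1.28, 1.51 and 1.70. A common correlation throughout gives 3.0.

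**The case against.** **The unused visits do not cause the bias.** A reader might infer that it comes from discarding bi-weekly data. It comes from using the crossover score as Group 1's UA baseline, and a single end-of-period comparison would remove it. The bi-weekly scores add precision and show whether reversal is complete. This objection stands.

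**The test itself is not undermined.** A reader might infer invalid p-values or lost power. The documents do not support either: the bias is proportional to the true effect, and the stated power reproduces.

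**50% is the full-reversal case.** This also stands. It is nonetheless the case that the protocol predicts, although Preliminary Studies does not give the number followed to one month.

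**The visits are not named.** The statistical text does not say which bowel visits are pre and post. One value each side of each arm is the plain reading, supported by the full battery being placed at baseline and after each arm, but it is an inference.

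**A missed final visit.** A reader might infer that such a participant is dropped. The plan gives no missing-data rule either way, so this cannot be claimed.

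**A late-window mean could err the other way.** The aim is the effect by three months, and Preliminary Studies says improvement continued through all sessions. If improvement were linear to −9 at week 12 (an assumption), weeks 8, 10 and 12 give −6, −7.5 and −9. Their mean is −7.5, about 17% too small. That rules out the three-visit mean as the main contrast.

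**Conclusion.** The concern holds for the effect size. As written, the bowel contrast overstates a true effect by half the fraction of benefit that Group 1 loses during UA: 12.5% to 37.5% for reversal of 25% to 75%, and 50% for the full reversal that the protocol expects. This rests on the plain reading of pre and post, equal group sizes, no other change over time, and a Group 2 that is stable under UA. The 10Q BFS figures use pilot means from 8 participants, but the percentage excess on the difference scale does not depend on them.

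The harm is to the estimate and to any judgement of it against the 25% goal. Type I error and the stated power are unaffected. The precision ratios of 1.3 to 1.7 (up to 3) rest on assumed correlations and compare a three-visit mean with one late visit; they do not measure a gain over the planned change-score test.

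**What to change.** For 10Q BFS and BSS, replace the change-score contrast with WALK versus UA levels at the end of each period (about week 12). Estimate it from a repeated-measures mixed model on all bi-weekly scores, with arm, visit, arm-by-visit, period, sequence, site, study-entry score and a within-participant correlation structure. Name the visits. The crossover score should enter as the last outcome of the first period, never as the baseline of the second.

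Report the mean of the last three visits as a sensitivity analysis, noting that it may dilute the effect if improvement continues to week 12.

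Plot Group 1's UA scores by visit. The level contrast assumes that reversal is complete by the end of UA, and a sequence term alone does not correct for a shortfall. If the return is incomplete, report that the level contrast is conservative.

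Cost: SAP wording and analysis time, with no new visits, and a reported effect that is likely to be smaller.

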5. Total body fat mass is hypothesized to be reduced on average by 9 ± 7 percent (an average of 1.9 ± 1.2 kg decrease from baseline).

Exploratory Hypotheses:

1. In Group 1 (WALK first), the bowel improvement changes will return to baseline values by one month of the UA arm.
2. In Group 1 (WALK first), the body fat mass and percent changes will return to baseline values by 3 months of the UA arm.
3. Associated with increased activity, there will be improved autonomic/cardiovascular function (vagal tone) as measured by the high frequency component of the holter monitor recordings and the tolerance to orthostatic challenge.
4. Associated with increased activity and fat mass loss, there will be statistically significant improvement in HDL-c, HOMA-IR, serum total testosterone and estradiol levels
5. Quality of life (using select SCI-QOL item banks) will be reported to be improve after in the WALK arm, but not for the UA arm

Safety concerns with the use of the exoskeletal devices will continue to be evaluated. Any serious (SAEs) or adverse events (AEs) will be recorded and reported the appropriate oversight bodies.

Study Design

Research design: A Phase III randomized clinical trial (RCT) will be performed using a crossover design and employing an exoskeletal-assisted walking intervention. The experimental arm will be compared to a usual activities (UA) arm, as the control, in 132 persons with chronic SCI (>6 month post injury) who are wheelchair-dependent for outdoor mobility in the community. Eligible participants will be randomized (within site) to one of two groups for 12 weeks (three months): Group 1 (n=32) will receive exoskeletal-assisted walking (WALK) first for 12 weeks then crossover UA for a second 12 weeks; Group 2 (n=32) will receive UA first for 12 weeks then cross-over to the WALK arm for 12 weeks of training. The WALK arm will consist of supervised exoskeletal-assisted walking training, three sessions per week (4-6 h/week) for 36 sessions for their second 12-week period. The UA arm will consist of identification of usual activities for each participant, encouragement to continue with these activities and attention by study team members throughout the 12-week UA arm. These activities will be recorded in a weekly log. A fixed answer format will be used to capture this information.

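### The protocol sets enrolment at 132, but its groups, its site quotas and the power calculation all give 64

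*Protocol*

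**What the plan says.** The figure of 132 appears twice in the protocol, each time beside a breakdown.

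- **Study Design, Research design.** The two arms are to be compared "in 132 persons with chronic SCI". The same paragraph continues: "Eligible participants will be randomized (within site) to one of two groups". It then sizes them: "Group 1 (n=32) will receive exoskeletal-assisted walking (WALK) first for 12 weeks" and "Group 2 (n=32) will receive UA first for 12 weeks".
- **Expected withdrawal rates.** After reporting that three of 13 pilot participants withdrew, the protocol says: "As such a total of 132 participants will be enrolled as follows: JJPVAMC (n=28, T3 and below), KFRC (n=16, T2 and above"). The sentence closes with a third site, UMROI, at 20.

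Table 4, which follows, gives the same three site quotas and a total of 64. Its title labels it as the original schedule.

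The primary power calculation, worded the same in the protocol and the SAP, reads "there is 100% power (alpha=5%, double sided Z-power=5.6) with 13 of 63 (20%) versus 38 of 64 (60%) achieving the goal". After 25% attrition it gives "alpha=5%, double sided Z-power=4.53), with 10 of 48 (20%) at session 12 versus 29 of 48 (60%) of the participants". The secondary power calculation, also in both documents, states only the number left after 25% dropout, which is 48. The SAP does not mention 132.

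**The concern.** The enrolment sentence presents three site quotas as the make-up of 132, and they do not add up to it. The design paragraph does the same with two groups. Nothing in either document allocates 132 people to sites, groups or devices.

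A reader cannot tell when recruitment is complete. Randomisation is blocked within site, yet the site quotas cover only 64. If 132 is the randomised number, the planned device training roughly doubles. The protocol reports one Ekso unit at KFRC and a quota of 16 there. The primary results are percentages with 95% confidence intervals, so their precision also depends on which number applies.

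**Working it through.** **Inputs.** Total 132 (Research design; Expected withdrawal rates). Groups 32 and 32 (Research design). Sites 28, 16 and 20 (Expected withdrawal rates). Rates 20% and 60% for the TUG goal, two-sided alpha 5%, sample sizes 64 and 48, Z-powers 5.6 and 4.53 (Power Calculation, both documents). Pilot withdrawal 3 of 13. Up to 36 WALK sessions per person.

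**Step 1: add the parts.**
- Groups: 32 + 32 = 64.
- Sites: 28 + 16 + 20 = 64.
- Table 4, as supporting evidence only: by group 14 + 8 + 10 = 32 each; by year 12 + 18 + 18 + 16 = 64.
- Gap: 132 − 64 = 68; ratio 132/64 = 2.06.

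**Step 2: reproduce the printed Z-powers.** The documents name a one-sample method but print no formula. Taking 60% as the reference proportion and 20% as the alternative:

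Z-power = [0.4·√n − 1.96·√(0.6 × 0.4)] / √(0.2 × 0.8)

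| n | Z-power | Printed |
|---|---|---|
| 47 | 4.46 | |
| 48 | 4.53 | 4.53 |
| 49 | 4.60 | |
| 63 | 5.54 | |
| 64 | 5.60 | 5.6 |
| 65 | 5.66 | |
| 99 | 7.55 | |
| 132 | 9.09 | |

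Worked for n = 64: (3.200 − 0.960)/0.4 = 5.60. Allowing for rounding, a printed 5.6 (5.55 to 5.65) needs n between 63.2 and 64.8, and a printed 4.53 needs n between 47.96 and 48.10. The only whole numbers that fit are 64 and 48. The denominator of 63 for the session-12 count does not fit and looks like a slip; nothing turns on it, since 13/63 = 20.6% and 13/64 = 20.3%.

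With the two percentages swapped, the formula gives 4.93 at 64, 4.06 at 48 and 7.78 at 132. That matches neither printed value, and 132 fits under neither orientation.

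**Step 3: test whether attrition explains 132.**
- 64 × 0.75 = 48, the number in the power text. The secondary calculation's 48 likewise implies 48/0.75 = 64.
- Inflating 64 for 25% loss: 64/0.75 = 85.3, so 86.
- Inflating 64 for the pilot rate: 64/(1 − 3/13) = 83.2, so 84.
- Loss needed to get from 132 to 64: 1 − 64/132 = 51.5%.
- 132 less 25%: 132 × 0.75 = 99, which appears nowhere.

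**Step 4: what depends on the answer, if 132 is the randomised number.**
- WALK sessions with no withdrawals: 132 × 36 = 4,752 against 64 × 36 = 2,304, a difference of 2,448.
- Half-width of a 95% interval at 60% success. The documents name no interval method, so two are shown. Wald is 1.96·√(0.24/n).

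| | 64-person plan | 132-person plan |
|---|---|---|
| No attrition (n = 64, 132): Wald | 12.0 points | 8.4 points |
| No attrition: Wilson | 11.7 | 8.2 |
| 25% attrition (n = 48, 99): Wald | 13.9 | 9.7 |
| 25% attrition: Wilson | 13.4 | 9.5 |

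- One-sample power for 20% against 60% is above 99.99% at 48, 64, 99 and 132.

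**The case against.** **No inference changes.** Power is near 100% at either number, no hypothesis or test depends on which is right, and the SAP is consistent on 64 and 48 apart from the stray 63. This stands, and it is why the point is not a power problem. It does not remove the contradiction in the stated enrolment target.

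**A later expansion.** Table 4 is labelled as the original schedule, which suggests that the target was raised to 132 and the old breakdown left behind. This may well be how the mismatch arose, but the label can excuse only the table. The enrolment sentence and the design paragraph are current text, carry no such label, and still pair 132 with parts that sum to 64.

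**Allowance for withdrawals.** The enrolment sentence follows directly from the discussion of withdrawals, so 132 might be an inflated figure. Neither the 25% allowance nor the pilot rate brings 64 anywhere near 132.

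**A count of people consented or screened.** The design paragraph randomises eligible participants, which leaves this reading just open. Support is thin: neither document says it, the enrolment sentence presents the site quotas as the make-up of 132, and the design paragraph describes the comparison itself as made in 132 people.

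**Conclusion.** The enrolment figure is wrong as written: 132 cannot be the sum of either breakdown given for it. The groups, the site quotas and both printed Z-powers agree on 64, so the power calculation was run on 64. The Z-power check rests on the reconstructed one-sample formula with 60% as reference, and both printed values match it to their printed precision.

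The target is ambiguous by 68 people (2.06-fold). The documents do not show which number is intended. The consequences for device sessions (up to 4,752 against 2,304) and for precision (Wald half-width 9.7 against 13.9 points after 25% attrition) apply only if 132 people are to be randomised. If 132 counts people screened, 64 are exposed either way and only the wording is at fault. Under the plan's own assumptions, no power is lost in any case.

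**What to change.** State one randomised number in the Research design and Expected withdrawal rates paragraphs. Bring the groups, site quotas, Table 4, attrition allowance and power text in both documents into line with it.

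- **If 64 is intended:** replace 132 with 64 in both places and correct the denominator of 63 to 64. This is a text change. If sites are already working towards 132, however, it more than halves the target, and both documents say that fewer participants would prevent many of the exploratory questions from being asked. The sponsor should confirm that those aims still stand.
- **If 132 randomised is intended:** restate the groups (66 each under equal allocation), give site and device quotas that sum to 132, update the schedule, and redo the power and attrition figures (99 after 25% loss). This covers 68 more people than the printed quotas and up to 2,448 more WALK sessions, so site and device capacity must be re-planned.
- **If 132 counts people consented or screened:** say so, keep 64 as the randomised number, and correct the 63. This is a text change only.
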